14.2 Adverse Events

An Adverse Event (AE) is defined as any untoward medical occurrence associated with the use of a drug in humans, whether or not the event is considered drug-related. All AEs will be coded using the MedDRA version 23.0.

Treatment-emergent adverse events (TEAE) are defined as any event that occurs or worsens on or after the day that randomized study treatment is initiated. It is not anticipated that any AEs will occur before treatment. However if in the unlikely event an AE recorded in the eCRF which began prior to treatment will not be included in the summary tables but will be included in the AE data listings.

Severity of an AE is defined as a qualitative assessment of the degree of intensity of an AE as determined by the Investigator or reported to him/her by the subject. The assessment of severity is made irrespective of relationship to study drug or seriousness of the event and should be evaluated according to the following scale:

- **Mild** - Events require minimal or no treatment and do not interfere with the subject's daily activities.
- **Moderate** - Events result in a low level of inconvenience or concern with the therapeutic measures. Moderate events may cause some interference with functioning.
- **Severe** - Events interrupt a subject's usual daily activity and may require systemic drug therapy or other treatment. Severe events are usually potentially life-threatening or incapacitating.

The relationship of each AE to the study drug should be determined by the Investigator using these explanations:

- **Definitely Related** – Evidence indicates a reasonable temporal sequence of the event with the study drug administration exists or that the association of the event with study drug administration is unknown and the event is not reasonably supported by other conditions such that:
 - There is a clinically plausible time sequence between onset of the AE and study treatment administration; and/or
 - There is a biologically plausible mechanism for study treatment causing or contributing to the AE; and
 - The AE cannot be reasonably attributed to concurrent/underlying illness, other drugs or procedures.

- **Potentially Related** – Evidence indicates a possible relationship to the study drug such that:

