 - The event occurs within a reasonable period of time relative to the treatment that makes a causal relationship possible, but plausible explanations may also be provided by other causes such as other drugs, products, chemicals, underlying disease, environment, etc.
 - The event is possibly related to the study treatment.
- **Not Related** – Evidence indicates no plausible direct relationship to the study drug such that:
 - A clinically plausible temporal sequence is inconsistent with the onset of the AE and drug administration; and/or
 - A causal relationship is considered biologically implausible.
 - The AE can be attributed to concurrent/underlying illness, other drugs, or procedures.

Definitely and potentially related TEAEs are considered treatment-related TEAEs.

An AE or suspected adverse reaction is considered "serious" if, in the view of either the investigator or sponsor, it results in any of the following outcomes: death, a life-threatening AE, inpatient hospitalization or prolongation of existing hospitalization, a persistent or significant incapacity or substantial disruption of the ability to conduct normal life functions, or a congenital anomaly/birth defect. Important medical events that may not result in death, be life-threatening, or require hospitalization may be considered serious when, based upon appropriate medical judgment, they may jeopardize the participant and may require medical or surgical intervention to prevent one of the outcomes listed in this definition. Serious adverse events include drug deficiencies that might have led to a SAE if a) suitable action had not been taken or b) intervention had not been made or c) if circumstances had been less fortunate.

A planned hospitalization for a pre-existing condition without a serious deterioration in health is not considered to be a SAE. Hospitalization for less than 24 hours is not considered a SAE unless the precipitating event was unanticipated and also related to the investigational drug.

Events that are considered sight-threatening in the opinion of the investigator will be considered SAEs.

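### For hospital stays under 24 hours, SAP 14.2 lets causality and expectedness decide whether an event is an SAE, and it counts near-miss drug deficiencies as SAEs without requiring an AE

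*SAP*

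**What the plan says.** All the relevant text is in SAP 14.2 (Adverse Events).

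- An AE is "any untoward medical occurrence associated with the use of a drug in humans, whether or not the event is considered drug-related".
- An AE or suspected adverse reaction is serious if the investigator or the sponsor considers that it led to one of the listed outcomes. One of these is "inpatient hospitalization or prolongation of existing hospitalization". No length of stay, causality or expectedness is attached.
- Two exceptions for hospitalization follow. One covers planned admissions for a pre-existing condition. The other reads: "Hospitalization for less than 24 hours is not considered a SAE unless the precipitating event was unanticipated and also related to the investigational drug".
- The definition also extends to products: "Serious adverse events include drug deficiencies that might have led to a SAE", with a last limb that applies "if circumstances had been less fortunate".
- It closes with an unconditional rule: "Events that are considered sight-threatening in the opinion of the investigator will be considered SAEs".

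Causality is assigned by the investigator on a three-level scale, and the upper two levels together count as treatment-related. The SAE category is then used in three outputs: the overall TEAE summary, a table of treatment-emergent SAEs and a listing of all SAEs.

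**The concern.** Seriousness describes what happened to the subject. Causality and expectedness are separate judgements. The SAP keeps them apart in its main criterion, and it also has severity graded without regard to drug relationship. The short-stay sentence joins them again: two subjects with the same 20-hour admission can get different SAE flags because one event was judged related and the other was not.

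This matters because the primary safety endpoint in SAP 2.1 already rests on treatment-related effects. The SAE table is where a reader looks for a comparison of serious outcomes that does not pass through a causality call. For short stays it does not fully provide one.

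The deficiency clause has the opposite problem. It admits something to the SAE category that need not have happened to any subject, so the category no longer sits inside the AEs.

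**Working it through.** The SAP states no figure on this point, so there is none to reproduce. The check is a comparison of rules, followed by a scale calculation.

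**Step 1: short inpatient stays.** Take an AE that results in an inpatient stay under 24 hours and meets no other seriousness criterion. Cross the two judgements named in the short-stay sentence.

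| Related | Unanticipated | Main criterion | Short-stay sentence |
|---|---|---|---|
| Yes | Yes | SAE | SAE |
| Yes | No | SAE | Not an SAE |
| No | Yes | SAE | Not an SAE |
| No | No | SAE | Not an SAE |

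The main criterion gives 4 of 4 serious; the short-stay sentence gives 1 of 4. Both unrelated cells are lost, and so is the related but anticipated cell.

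**Step 2: who decides, and how clearly.** Seriousness may be judged by the investigator or the sponsor, but relatedness is given to the investigator. For a short stay, a not-related call therefore appears to settle seriousness as well. The boundary of that call is not sharp: underlying disease as an alternative explanation appears under both the potentially related and the not related categories. The sentence does not say whether related includes potentially related, although the section groups the two elsewhere. The supplied text does not define unanticipated.

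**Step 3: drug deficiencies.** An AE needs an untoward medical occurrence, and seriousness is defined as a property of an AE or suspected adverse reaction. A deficiency caught before it affects anyone involves no such occurrence, so it is not an AE. If it might have led to an SAE in less fortunate circumstances, the deficiency clause makes it an SAE. The two rules give an SAE that is not an AE.

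**Step 4: scale.**
- Input from SAP 5: about 209 subjects randomized per arm.
- One reclassified subject: 1/209 = 0.48 percentage points of SAE incidence in that arm.
- The documents give no SAE rate. Assume 0.5% to 2%: 0.005 × 209 = 1.0 and 0.02 × 209 = 4.2, so about 1 to 4 subjects per arm.
- One event as a share of an arm's count: 1/4 = 25% up to 1/1 = 100%.

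Safety tables use dosed subjects, so the true denominator could be slightly below 209.

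**The case against.** The best defence is that a specific exception after a general rule is ordinary drafting. The subject of the sentence is hospitalization, it follows a parallel exception for planned admissions, and it most naturally qualifies the hospitalization criterion alone. That is right, and it disposes of one tempting reading. A reader might infer that a short stay cancels the life-threatening, important-medical-event or sight-threatening criteria. The text gives no order of precedence, so the wording does not rule this out. But important medical events expressly need no hospitalization, and the sight-threatening rule that follows is unconditional. On the natural reading those criteria still apply. What survives is that the exception itself turns on causality and expectedness.

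A reader might also infer that unrecognized drug effects vanish from the randomized comparison. They do not. SAP 14.2 tabulates ocular and non-ocular TEAEs by arm, system organ class and preferred term, whether or not they are judged related. A short admission judged unrelated stays there and loses only its serious flag. Causality is judged under masking (SAP 4.2), so no bias between arms is shown.

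On deficiencies, a reader might infer that every product fault inflates the SAE table. The clause covers only faults that might have led to an SAE. A fault that is not an AE may not enter a summary or table built on TEAEs; the listing of all SAEs is the one place it would clearly appear.

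Finally, seriousness is decided during conduct. The supplied protocol has only a synopsis, schema and redacted schedule, and the SAP claims to supersede only the protocol's statistical methods. Editing the SAP alone may not change what sites report. That stands, and it is why the two documents must be aligned.

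**Conclusion.** The point holds within limits. For inpatient stays under 24 hours, the SAE flag depends on causality and expectedness, contrary to the unconditional criterion in the same definition. The consequence is possible under-counting and inconsistent classification of short-stay SAEs. It does not make the SAE count as a whole depend on causality. Separately, a near-miss deficiency with no untoward occurrence is classed as an SAE without being an AE, and its place in the outputs beyond the listing is unclear.

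The relative size is large only because SAE counts are probably small, and that range rests wholly on the assumed 0.5% to 2% rate. The documents do not show that any short admission or deficiency is likely. No SAE hypothesis test is described in the supplied SAP, and the primary and secondary efficacy analyses, alpha and power are untouched.

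**What to change.** Reconcile the sentences in SAP 14.2 so that seriousness does not depend on causality or expectedness.

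1. Delete the whole under-24-hour sentence. Alternatively, limit it to visits without inpatient admission that meet no other seriousness criterion, sight-threatening included, whatever the causality. Removing only the condition that begins with unless would be worse: it would exclude every short stay and take the grid above from 1 of 4 serious to 0 of 4.
2. List drug deficiencies without an untoward medical occurrence separately from SAEs. A deficiency that did cause an AE is classified by that AE.
3. Align the wording with the protocol's SAE section, which is not in the supplied text, so that the definition used at the sites and the one used in the tables agree.

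The cost is a wording change in the SAP and, where needed, in the protocol. A few more short admissions may be reported as SAEs.

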14.3 Corrected Distance Visual Acuity

For CDVA testing, subjects will wear their own spectacles or may use a pinhole occluder for correction using the Early Treatment Diabetic Retinopathy Study (ETDRS) Fast procedure under standard illumination. The subject will be asked to focus on an ETDRS visual acuity chart 4 meters away, checking one eye at a time. The number of letters read correctly will be used to compute the subject's logarithm of the minimum angle of resolution (logMAR) score for CDVA. The procedure used will be consistent with the recommendations provided for using the ETDRS-Fast method.

Visual acuity should be evaluated near the beginning of each study visit (i.e., prior to slit lamp examination). Subjects should use their most recent correction to attain their CDVA; if they forget their spectacles, this prescription can be placed in a trial frame or a pinhole can be used.

The observed and change from Baseline CDVA will be summarized for each eye using continuous descriptive statistics by visit for each treatment group. A subject listing of visual acuity will also be produced. This listing will include a variable that indicates if a subject had a visual acuity change from Baseline of ≥ 0.22 on the logMAR scale.

14.4 Slit-Lamp Biomicroscopy Examination

A slit-lamp biomicroscopy examination will be performed and the following structures will be assessed for pathology defined as normal, abnormal NCS, or abnormal CS:

- Eyelids and lashes (i.e., meibomian glands, lid margin, puncta, lashes)

- Cornea
- Conjunctiva
- Anterior chamber
- Iris
- Crystalline lens (Lens Opacities Classification System III for grading)
- Eyelids and Eyelashes

The results will be summarized using counts and percentages for each treatment group and for all actively treated subjects at each visit for each eye. Percentages will be based on the number of subjects in each treatment group with responses. Shift tables for the slit-lamp biomicroscopy parameters will also be provided comparing each follow-up visit to Baseline. A subject listing of the slit-lamp biomicroscopy parameters will also be produced.

14.5 Dilated Fundus Examination

An examination of the posterior segment of the eye with dilation will be performed using indirect ophthalmoscopy. Pupils should be dilated adequately to perform a thorough fundus evaluation. The following structures will be assessed for pathology defined as normal, abnormal NCS, or abnormal CS:

- Vitreous
- Optic nerve
- Macula
- Retina
- Choroid

The results will be summarized using counts and percentages for each treatment group at each visit for each eye. Percentages will be based on the number of subjects in each treatment group with responses. Shift tables for the dilated fundus exam parameters will also be provided comparing each follow-up visit to Baseline. A subject listing of the dilated fundus exam parameters will also be produced.

14.7 Intraocular Pressure

Subjects' IOP will be assessed by applanation tonometry in each eye at each visit. Results will be taken from a single measurement and will be recorded in mmHg.

The IOP values and changes from Baseline for each eye will be summarized using continuous descriptive statistics by visit and eye for each treatment group. A subject listing of IOP will also be produced. This listing will include a variable that indicates if a subject had an IOP increase from Baseline of ≥ 6 or ≥ 10 mmHg.

11. **What is the primary purpose of the *Journal of Clinical Endocrinology and Metabolism*?**

11. **What is the primary purpose of the *Journal of Clinical Endocrinology and Metabolism*?**

10.1007/s00339-010-0640-1

11. **What is the primary purpose of the *Journal of Clinical Endocrinology and Metabolism*?**

10.1007/s00339-010-0637-0

10.1007/s00339-010-0633-2

10.1007/s00339-010-0634-2

For more information, contact the Office of the Vice President for Research and Economic Development at [contact] or [contact].

For more information, contact the Office of the Vice President for Research and Economic Development at [contact] or [contact].

14.9 Urine Pregnancy Test

At Screening and at the final treatment visit, a urine pregnancy test should be administered to women of childbearing potential (WOCBP). WOCBP includes any females who have experienced menarche and who have not undergone successful surgical sterilization (hysterectomy, bilateral tubal ligation or bilateral oophorectomy) or are not postmenopausal at least 12 months since last menses. The pregnancy test result should be recorded as positive or negative on the eCRF. The results will be summarized using counts and percentages for each treatment group. Percentages will be based on the number of subjects in each treatment group with responses. A subject listing of the urine pregnancy test result will also be produced.

For more information, contact the Office of the Vice President for Research and Economic Development at [contact] or [contact].

For more information, contact the Office of the Vice President for Research and the Office of the Vice President for Student Affairs.

10. *Journal of the American Statistical Association*, 1980, 75, 362-375.

10.1007/s00332-010-9000-0

For more information, contact the Office of the Vice President for Research and Economic Development at [contact] or [contact].

For more information, contact the Office of the Vice President for Research and Economic Development at [contact] or [contact].

For more information, contact the Office of the Vice President for Research and the Office of the Vice President for Student Affairs.

For more information, contact the Office of the Vice President for Research and the Office of the Vice President for Student Affairs.

14.12 Corneal Staining

Corneal Staining is assessed at Days 1, 8, 15, 22, 43 and 57 (Cohort 2 only). The following will be assessed:

- Inferior
- Superior
- Central
- Temporal

- Nasal
- Corneal Sum

The observed values and change from baseline for corneal sum will be summarized for each eye using continuous descriptive statistics for each treatment group. All other measures will be summarized using counts and percentages for each treatment group at each visit. Percentages will be based on the number of subjects in each treatment group with responses. A subject listing of the corneal staining will also be produced.

15. Interim Analyses

No interim analysis is planned.
